3.3 Cabozantinib Dose Modifications, Interruptions, and Discontinuation

Subjects will be monitored for AEs from the time of signing informed consent through their last follow-up visit (30 days after the date of the last dose of cabozantinib treatment.) Subjects will be instructed to notify their physician immediately at the onset of any AE. Causality assessment of AEs will be determined by the investigator. AE severity will be graded by the investigator in accordance with CTCAE v.4.0.

The following should be taken into consideration in decisions regarding dose modifications (reductions or interruption):

- As a general approach all AEs should be managed with supportive care at the earliest signs of toxicity considered related to the study treatment. Should this be ineffective, dose interruptions and/or reductions should be considered to prevent worsening of toxicity.
- Dose modification criteria for cabozantinib are shown in Table 3-3. Dose interruptions and/or reductions should be implemented for unacceptable toxicity. Doses may be modified at any time while a subject is on treatment.

The assigned starting dose for cabozantinib is 40 mg/day. 1 dose reduction level of cabozantinib is permitted to 20 mg/day (see Table 3-2).

- Dose reductions or interruptions may also occur in the setting of lower grade toxicity than defined in Table 3-3, if the investigator feels it is in the interest of a subject's safety and will optimize drug tolerability.
- Interruption of cabozantinib treatment for cabozantinib-related AEs may occur at any time per investigator discretion. If treatment is interrupted due to related AEs for more than 6 weeks, cabozantinib should be discontinued unless there is unequivocal evidence that the subject is benefitting. In this situation, a subject may be able to restart therapy with a dose reduction upon resolution of the toxicity per the discretion of the investigator.
- Dose interruptions for reason(s) other than related AEs (eg, surgical procedures) can be longer than 6 weeks per the discretion of the investigator.

Table 3-2: Dose Reductions of Cabozantinib

Guidelines for the management of specific AEs are provided in Section 3.3.2.

When cabozantinib or pembrolizumab are discontinued for reasons deemed to be related to one or the other agent, the protocol calls for the discontinuation of both agents until and when the toxicities have reached a tolerable level (as specified in the dose modification sections) at which time both agents will be re-initiated. Patients who have interruption of both agents for more than 6 consequential weeks will be removed from the study; response assessment for these patients will still be assessed if available; in addition to assessment of OS and PFS based on the intent to treat analysis principle.	Assigned dose	First Dose Level Reduction
	40-mg cabozantinib oral qd	20-mg cabozantinib oral qd

Table 3-3: Dose Modifications of Cabozantinib for Treatment-Related AEs

CTCAE v.4.0 Grade	Recommended Guidelines for Management ^a
Grade 1 AEs	Add supportive care as indicated. Continue cabozantinib treatment at the current dose level if AE is manageable and tolerable.
Grade 2 AEs which are tolerable and are easily managed	Continue cabozantinib treatment at the current dose level with supportive care.
Grade 2 AEs which are intolerable and cannot be adequately managed	At the discretion of the investigator, cabozantinib should be dose reduced or interrupted. Note: It is recommended that dose holds be as brief as possible.
Grade 3 AEs (except clinically non-relevant laboratory abnormalities)	Cabozantinib should be interrupted unless the toxicity can be easily managed with a dose reduction and optimal medical care. Note: It is recommended that dose holds be as brief as possible.
Grade 4 AEs (except clinically non-relevant laboratory abnormalities)	Subjects should have cabozantinib interrupted immediately. Discontinue cabozantinib unless the following criteria are met: 
• Subject is deriving clear clinical benefit as determined by the investigator and agreed by the Sponsor• Toxicity can be managed with a dose reduction following recovery to Grade 1 (or baseline) and optimal medical care

AE, adverse event.

Note: The dose delay and modification criteria for specific medical conditions are provided in Section 3.3.2. For re-treatment criteria of study treatment after a dose hold see Section 3.3.1.1.

^a Study treatment dose adjustment is only needed if the toxicity was deemed related to cabozantinib treatment or had an unclear relationship to cabozantinib treatment.

Please refer to Sections 3.3.2.2 – 3.3.2.19 for the expected adverse events and management guidelines for cabozantinib.

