1.2.3.2.1 Adverse Events

In the pooled analysis of 2410 patients treated with single-agent cabozantinib, the most common AEs ($\geq 5\%$ incidence) reported at severity of Grade 3 and above were fatigue (15.3%), hypertension (13.7%), diarrhea (10.4%), anemia (8.3%), PPES (7.7%), asthenia (6.8%), pulmonary embolism (6.1%), and decreased appetite (5.6%).

The most frequently ($\geq 20\%$ incidence) observed AEs reported as related to cabozantinib were diarrhea (53.9%), fatigue (53.2%), decreased appetite (44.8%), nausea (44.1%), PPES (34.0%), weight decreased (27.8%), vomiting (25.4%), dysgeusia (25.1%), hypertension (25.0%), and dysphonia (21.6%).

Based on AE data available as of the data cutoff dates, 533 subjects (22.1%) in the pooled single-agent cabozantinib studies discontinued cabozantinib due to an AE (including events related to disease progression). The most frequently reported AEs ($\geq 1\%$ of subjects) that led to treatment discontinuation were fatigue (2.9%), general physical health deterioration (1.8%), asthenia (1.3%), decreased appetite (1.2%), nausea (1.0%), and diarrhea (1.0%).

Further details can be found in the Investigator’s Brochure.

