3.3.2 Warnings and Precautions and Guidelines for the Management of Adverse Events

The most frequent adverse events experienced by $\geq 20\%$ of subjects treated with cabozantinib were diarrhea, fatigue, nausea, decreased appetite, vomiting, weight decreased, PPES, constipation, hypertension, dysgeusia, dysphonia, and asthenia.

Adverse events associated with laboratory abnormalities experienced by $\geq 5\%$ of subjects treated with cabozantinib include anemia, AST increased, ALT increased, hypothyroidism, hypokalemia, hypomagnesemia, thrombocytopenia, hypocalcemia, hypophosphatemia, lipase increased, lactate dehydrogenase (LDH) increased, neutropenia, ALP increased, hyponatremia, and leukopenia. Mild to moderate QTc interval prolongation (10-15ms) has also been observed with a QT interval calculated by the Fridericia formula (QTcF) not exceeding 500 ms.

Subjects may also experience medically important but less frequent adverse events including arterial and venous thrombotic AEs (eg, DVT, pulmonary embolism [PE], transient ischemic attack [TIA], and myocardial infarction [MI]), severe hemorrhagic events, proteinuria, wound healing complications, GI perforation, abscesses including intra-abdominal and pelvic abscess,

GI and non-GI fistulae formation, osteonecrosis, and reversible posterior leukoencephalopathy syndrome (RPLS).

Cabozantinib treatment should be permanently discontinued for the following adverse events: visceral perforation or fistula formation, severe hemorrhage, serious arterial thromboembolic events, nephrotic syndrome, malignant hypertension, hypertensive emergency, persistent uncontrolled hypertension despite optimal medical management, osteonecrosis of the jaw (ONJ), and RPLS.

Guidelines for the management of AEs (ie, dose interruptions and dose reductions) are presented in the next sections. Each dose reduction of cabozantinib should be to one dose level lower than the current dose. Dose reductions of more than one dose level are acceptable per Investigator judgment. All AEs should also be managed with supportive care at the earliest signs of toxicity. Adverse reactions are presumed to be attributable to study drug. Adverse events classified as “not related” are defined as AEs that are, without question, not associated with the study treatment and definitely attributable to another cause.

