3.3.2.3 Hepatobiliary Disorders

Elevations of ALT, AST, and bilirubin have been observed during treatment with cabozantinib. It is recommended that subjects with elevation of ALT, AST, and/or bilirubin have more

frequent laboratory monitoring of these parameters. If possible, hepatotoxic concomitant medications should be discontinued in subjects who develop increased values of ALT, AST, or bilirubin.

Subjects on this study may enter with increased ALT/AST serum levels up to $2 \times$ ULN. Dose reductions of study treatment should be considered in any subject who develops drug-related Grade 2 elevated ALT, AST, or bilirubin lasting longer than 1 week. A subject who develops Grade ≥ 3 elevated ALT, AST, or bilirubin should have study treatment held and restarted at a reduced dose (see Table 3-2) after ALT, AST, and bilirubin levels resolve to at least Grade ≤ 1 or baseline. In subjects with recurrence of drug-related Grade ≥ 3 elevated ALT, AST, or bilirubin at the lowest dose level, study treatment should be discontinued. In subjects who develop ALT/AST elevations $> 3 \times$ ULN in combination with a bilirubin elevation $> 2 \times$ ULN without reasonable other explanation, drug-induced liver injury should be suspected and cabozantinib treatment interrupted. Reinstitution of study treatment after recovery of ALT, AST, and bilirubin to Grade 1 or baseline level is at the discretion of the investigator.

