Hyperglycemia, severe (Grade 3); also administer antihyperglycemics.

Hyperthyroidism, severe (grade 3) or life threatening (grade 4); manage with thionamides and beta-blockers as appropriate.

Hypophysitis, grade 2 (symptomatic); also administer corticosteroids (followed by a taper) and hormone replacement therapy if appropriate.

Hypoparathyroidism (Low levels of parathyroid hormone) (may occur rarely (<1%) which may result in low blood calcium and cause muscle cramps or spasms; fatigue or weakness; numbness, tingling or burning in fingertips, toes or lips

Nephritis, grade 2; also administer corticosteroids (prednisone 1 to 2 mg/kg/day [or equivalent] followed by a taper).

Pneumonitis, moderate (grade 2); also administer corticosteroids (prednisone 1 to 2 mg/kg/day [or equivalent] followed by a taper).

Other treatment-related toxicity, severe or grade 3; may require corticosteroids (based on severity). Upon improvement to grade 0 or 1, initiate corticosteroid taper and continue to taper over at least 1 month. Restart pembrolizumab if the adverse reaction remains at grade 0 or 1 following corticosteroid taper. May consider other systemic immunosuppressants if not controlled by corticosteroids (based on limited data).

Withhold (may resume upon recovery to grade 0 or 1 toxicity) or discontinue for:

Hyperthyroidism, severe (grade 3) or life-threatening (grade 4); manage with thionamides and beta-blockers as appropriate.

Hypophysitis, severe (grade 3) or life-threatening (grade 4); also administer corticosteroids and hormone replacement as appropriate.

Permanently discontinue for:

Adverse reactions that are life-threatening, persistent grade 2 or 3 adverse reaction (excluding endocrinopathies controlled with hormone replacement therapy) that does not recover to grade 0 or 1 within 12 weeks after the last pembrolizumab dose, or any recurrent severe or grade 3 treatment-related adverse reaction. Also administer corticosteroids (may consider other systemic immunosuppressants if not controlled by corticosteroids [based on limited data]).

Colitis, life-threatening (grade 4); also administer corticosteroids (prednisone 1 to 2 mg/kg/day [or equivalent] followed by a taper).

Immune mediated adverse reactions: Discontinue permanently if unable to reduce corticosteroid dose to prednisone \leq 10 mg/day (or equivalent) within 12 weeks.

Infusion-related reaction, grade 3 or 4.

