^m Only for select patients who have lack of prior progression at one year

ⁿ- A 2 days window for infusion of Pembrolizumab is allowed for logistic reasons- Every effort should be made to avoid interruption in Cabozantinib administration as a result of changes in Pembrolizumab schedule. A 2 day window for clinical labs and history & physical is also allowed for logistical reasons.

If the subject is unable to have a study assessment taken within the defined time window due to an event outside of his or her control (eg, clinic closure, personal emergency, inclement weather, vacation), the assessment should be performed as close as possible to the required schedule.

Regular tumor assessments should be performed in accordance to the guidelines in Section o to determine if PD is present.

The Treatment Period ends when a subject receives his or her last dose of study treatment; the subject then enters the Post-Treatment Period.

○ **Post-Treatment and End on Treatment Period**

Subjects will return to the study site 30 to 37 days after their last dose of cabozantinib, pembrolizumab or both to complete end-of-study assessments.

At the end of 24 months of treatment on the combination of pembrolizumab and cabozantinib, patients who are in continued response and who in the opinion of the investigators can continue to benefit from therapy will be given the options of either terminating therapy, or continuing on the combination with the use of the EASE program overlooked by Exelixis ; This program will provide commercial cabozantinib to patients who wish to continue therapy for an additional 12 months of treatment; patients who continue on the EASE program will be followed as per standard of care at the respective institutions.

Laboratory and physical examinations will be performed. Remaining study treatment will be returned by the subject, and treatment compliance will be documented. Additional follow-up will occur for subjects with AEs related to study treatment that are ongoing at the time of this visit, and for subjects with SAEs related to study treatment that occur after the time of this visit.

○ Laboratory Assessments

Laboratory panels are composed of the following:

Hematology	
 • WBC count with differential (including at minimum: neutrophils, basophils, eosinophils, lymphocytes, monocytes) • hematocrit • platelet count • RBC count • hemoglobin • ESR • reticulocytes

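### Section 3.3 re-initiates both drugs after a toxicity stop with no exception for a permanent stop, while other sections stop one drug for good and mostly do not address its partner

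*Combined protocol and SAP*

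**What the plan says.** **Joint rule.** Section 3.3 (paragraph at Table 3-2) applies when either agent is discontinued for toxicity attributed to one or the other. In that case "the protocol calls for the discontinuation of both agents until and when the toxicities have reached a tolerable level", and the sentence continues "as specified in the dose modification sections) at which time both agents will be re-initiated". It then adds: "Patients who have interruption of both agents for more than 6 consequential weeks will be removed from the study". Response data on removed patients are still used if available.

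**Permanent stops of cabozantinib.** Section 3.3.2 states: "Cabozantinib treatment should be permanently discontinued for the following adverse events: visceral perforation or fistula formation, severe hemorrhage", and the list goes on. Sections 3.3.2.10 (nephrotic syndrome), 3.3.2.15 (fistula and perforation) and 3.3.2.18 (serious rhabdomyolysis, RPLS) also end cabozantinib. Table 3-6 and Section 3.3.2.11 instead end all *study treatment* for certain events.

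**Permanent stops of pembrolizumab.** Section 3.4.1 has its own list, including AST or ALT above 5 x ULN, grade 3 or 4 infusion reactions and severe pneumonitis. It does not say what then happens to cabozantinib.

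**Withdrawals.** Section 2.7 takes a subject off *study treatment* for the conditions in Sections 3.3.2 and 3.3.2.1. It does not cite Section 3.4.1.

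**The concern.** The trigger word in Section 3.3 is the same word that the permanent-stop instructions use. A site that reads the sentence literally would bring both drugs back once toxicity settles, including a drug that another section has ended for that patient. A site that starts from the event sections would apply each one to its own drug and find no instruction for the other. One-drug stops are foreseen: the DLT definition in Section 2.2.1 refers to permanent discontinuation of either agent or both.

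Patient safety comes first, because restart instructions for the same event conflict. There is also a consequence for the data. Table 16-1 schedules tumor measurement every 9 weeks only in the column for patients taking study drugs, and after treatment it schedules it only at one year, for selected patients without earlier progression. The reading a site chooses therefore affects whether a late response or a progression is captured on schedule.

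**Working it through.** The plan gives no figure on this point, so the check sets the instructions side by side.

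**Step 1. Does Section 3.3 except permanent stops?** No. The cross-reference to the dose modification sections qualifies the tolerable level of toxicity. It does not say that restart depends on whether those sections allow it.

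**Step 2. Does Section 2.7 close the gap?** Only in part. It covers the cabozantinib conditions. However, it also gives the minimum dose of *study treatment* as 20 mg once daily, which can only be cabozantinib. Whether leaving *study treatment* also ends pembrolizumab is therefore unclear. For the pembrolizumab list there is no equivalent cross-reference, only the investigator's general discretion to withdraw a subject for an adverse event.

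**Step 3. ALT or AST above 5 x ULN.** Section 3.4.1 pairs this threshold with the same prednisone range (1 to 2 mg/kg/day) that its hepatotoxicity warning gives for grade 3 or higher hepatitis. I therefore take it to be the Grade 3 or higher range used in Section 3.3.2.3.

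| Place | Cabozantinib | Pembrolizumab |
|---|---|---|
| Section 3.3.2.3 | *Study treatment* "should have study treatment held and restarted at a reduced dose (see Table 3-2") after recovery | Not named; included only if *study treatment* means both |
| Section 3.4.1 | Not addressed | Permanently discontinued |
| Section 3.3 | Stopped, then re-initiated | Stopped, then re-initiated |

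Three courses follow, depending on which text a site puts first:
- Both drugs restart. This meets Section 3.3 and conflicts with Section 3.4.1.
- Neither restarts, and the patient is removed after more than 6 weeks. This meets Section 3.4.1 and the joint stop, but not the restart in Section 3.3.2.3.
- Cabozantinib restarts alone. This meets Sections 3.3.2.3 and 3.4.1 if *study treatment* means cabozantinib, but Section 3.3 does not provide for it.

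No course satisfies all three sections.

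**Step 4. Nephrotic syndrome.** The text of Section 3.3.2.10, like the list in Section 3.3.2, ends cabozantinib. Table 3-6, in the same section, ends all *study treatment*. The two agree only if that term means cabozantinib alone, and the plan does not define it.

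**Step 5. Link to the primary endpoint.** Section 2.1 defines ORR by RECIST 1.1 with no condition on which drug is being taken. Section 18 defines evaluable subjects as those who received therapy and had a follow-up scan. A response first seen after one drug has ended therefore counts. That follows from the definitions, but the plan does not state it as a choice.

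**The case against.** The strongest reply is that Section 3.3 is a hold rule: it speaks of a stop lasting until recovery, points to the dose modification sections and then refers to interruption. A careful reader would let a specific permanent stop override a general hold, and the notes around Table 3-3 send sites to Section 3.3.2 for specific conditions. This largely stands. A reader might infer that Section 3.3 orders restart of a drug that has been ended permanently, but the text does not expressly do so. The fault is a loose trigger word and a missing exception.

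Section 3.3 also does not permit single-agent continuation. A reader might infer that it does, but single-agent treatment arises only where a site follows an event section alone.

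On liver toxicity, it can be said that Section 3.3.2.3 restarts by way of Table 3-2, which lists only cabozantinib doses, so that it and Section 3.4.1 govern different drugs. That is a fair reading. It removes a direct conflict between those two sections but leaves each in tension with Section 3.3.

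Two further inferences are too weak to use:
- The follow-up wording in Section 16, "Subjects will return to the study site 30 to 37 days after their last dose of cabozantinib, pembrolizumab or both", does not show that one drug continues. A daily tablet and a 3-weekly infusion can have different last-dose dates even when stopped together.
- The pembrolizumab criterion "or any recurrent severe or grade 3 treatment-related adverse reaction" might be read as ending pembrolizumab for recurrent cabozantinib-related hypertension. It stands in pembrolizumab drug information and more naturally means reactions to that drug.

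Finally, counting later responses toward the assigned regimen is a usual treatment-policy approach and is not itself an error.

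**Conclusion.** The concern holds as a conflict between stated instructions plus a gap. The gap is partly covered by Section 2.7 for cabozantinib and open for pembrolizumab. It matters for safety and for uniform follow-up, and it can be corrected by wording.

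Its effect on ORR cannot be quantified from the documents. A reader might start from "533 subjects (22.1%) in the pooled single-agent cabozantinib studies discontinued cabozantinib due to an AE" and compute 0.221 x 34 = 7.5 patients, then 7.5 x 0.18 = 1.4 responses on pembrolizumab alone, against a decision boundary of 9 versus 10 responses. The documents do not support that sum:
- The 22.1% covers any adverse-event stop, including events related to progression, and not just the permanent-stop list.
- It comes from single-agent studies. Where the protocol gives a cabozantinib dose for such studies it is 60 mg or 140 mg, against a 40 mg start here.
- The sum assumes that every such patient continues pembrolizumab alone, which Section 3.3 does not permit, and that every response first appears after the stop.

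The conclusion rests on the wording alone. The liver example also relies on matching the 5 x ULN threshold to Grade 3 or higher, as explained above.

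**What to change.** By amendment:
- Reconcile Sections 2.7, 3.3, 3.3.2, 3.3.2.3, 3.3.2.10 (with Table 3-6), 3.3.2.11, 3.3.2.15, 3.3.2.18 and 3.4.1, so that each event carries one consistent instruction for each agent. Which clinical rule applies is for the sponsor to decide; none is proposed here.
- Define *study treatment* as cabozantinib, pembrolizumab or both wherever it is used, and state how the 9-weekly scan schedule applies once one agent has ended.
- Record a permanent-stop date and reason separately for each agent.
- Keep the primary ORR count unchanged, and add a supplementary listing of any response first documented after one agent was permanently stopped.

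The cost is amendment wording, one CRF field per agent and one listing.

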2 STUDY OBJECTIVES AND DESIGN

2.1 Study Objectives

The objectives of this study are as follows:

Primary Objectives:

To estimate the overall response rate (ORR) of patients with RM SCCHN who receive the combination of pembrolizumab and cabozantinib.

Secondary Objectives:

- To estimate the progression-free survival (PFS) of patients treated with the combination of pembrolizumab and cabozantinib.
- To further define the toxicities associated with these regimens in patients with SCCHN.

Exploratory Objectives:

- To identify potential biomarkers related to response to the combination of pembrolizumab and cabozantinib in patients with RM SCCHN. Specifically, to evaluate whether markers of angiogenesis, hypoxia, Met or pMet expression, or inflammatory activation can predict response to the combination or PFS.
- To gather exploratory clinical data on a potentially predictive set of biomarkers (potential biomarkers include MET expression by FISH, NGS and IHC/IHF of cMET, pMET, HGF, HER2, HER3 and heregulin mRNA level).
- To evaluate circulating cell free DNA (cfDNA) in plasma and its association with response to the combination or PFS.
- To evaluate potential neoantigens in the tumor DNA, their expression, and their association with response to the combination or PFS.
- Evaluate peripheral blood mononuclear cells (PBMC) for immune monitoring and their association with response to the combination or PFS.
- To determine a quantitative radiomics based on CT and/or PET images as a prognostic biomarker in recurrent or metastatic HNSCC.
 - To determine a computational pathology (or pathomics) based prognostic marker from standard digitized H&E images of the tumor in recurrent or metastatic HNSCC.
-

Endpoints

Primary Endpoint

ORR: The proportion of subjects with partial response (PR) or complete response

(CR) as defined by RECIST v1.1 response criteria.

Secondary Endpoints

PFS: The duration from date of treatment start to the date of objectively documented progression or death due to any cause, whichever status is recorded first.

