2.7 Withdrawals

Subjects may discontinue study treatment or withdraw their consent to participate in the study at any time without prejudice. The investigator may withdraw a subject from study treatment or from the study if, in his or her clinical judgment, it is in the best interest of the subject or if the subject cannot comply with the protocol.

In addition, any of the following conditions require discontinuation of the subject from study treatment:

- An AE or intercurrent illness that in the opinion of the investigator warrants the subject's withdrawal from study treatment;
- The investigator believes it is not in the best interest of the subject to continue on study
- Specific conditions described in the Management of Adverse Events Sections 3.3.2 and 3.3.2.1;
- Necessity for treatment with other anticancer treatment prohibited by protocol;
- Sexually active subjects who refuse to use medically accepted barrier methods of contraception (eg, male condom, female condom) during the course of the study and for 4 months after discontinuation of study treatment;
- Women who become pregnant or are breastfeeding;
- If the subject does not recover from his or her toxicities to tolerable Grade ≤ 2 within 6 weeks, the subject will have study treatment discontinued unless there is unequivocal evidence that the subject is benefitting. In this situation, a subject may be able to restart therapy with a dose reduction upon resolution of the toxicity and with agreement of the principal investigator / Sponsor;
- Request by regulatory agencies for termination of treatment of an individual subject or all subjects under the protocol;
- Significant noncompliance with the protocol schedule in the opinion of the investigator;
- The minimum dose of study treatment will be 20 mg once daily (qd). Subjects who cannot tolerate 20 mg qd will have study treatment discontinued;

- Progressive disease (PD) or the subject no longer experiences clinical benefit as determined by the investigator

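### Section 3.3 removes patients after more than 6 weeks off both drugs without the benefit exception allowed elsewhere, and Table 16-1 ties 9-weekly scans to being on drug although intent-to-treat PFS is promised

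*Combined protocol and SAP*

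**What the plan says.** **The 6-week limit appears three times.**

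- Section 2.7 (Withdrawals): if toxicity has not recovered to a tolerable grade of 2 or less within 6 weeks, "the subject will have study treatment discontinued unless there is unequivocal evidence that the subject is benefitting". The patient may then restart at a reduced dose "upon resolution of the toxicity and with agreement of the principal investigator / Sponsor".
- Section 3.3, bullet on interruptions for related AEs: after more than 6 weeks, "cabozantinib should be discontinued unless there is unequivocal evidence that the subject is benefitting". A reduced-dose restart is possible "upon resolution of the toxicity per the discretion of the investigator". The next bullet says that holds for other reasons, such as surgery, "can be longer than 6 weeks per the discretion of the investigator".
- Section 3.3, paragraph on joint interruption beside Table 3-2: if either drug is stopped for toxicity, both are stopped until it is tolerable. Then: "Patients who have interruption of both agents for more than 6 consequential weeks will be removed from the study". No exception is attached. The same sentence keeps response data where available, "in addition to assessment of OS and PFS based on the intent to treat analysis principle".

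**Imaging.** PFS runs from treatment start to "the date of objectively documented progression or death due to any cause" (Section 2.1, Endpoints). The synopsis (Tumor Assessments) and Section 2.2.1 ask for imaging every 9 weeks and do not limit this to patients on drug. Table 16-1 in Section 16 puts the 9-weekly tumor measurement and radiology entries in the column for cycles on study drugs. Section 16 ends the Treatment Period at the last dose. The 30-to-37-day visit and the 3-monthly follow-up carry no scan. The only later imaging is at one year: footnote m limits the Tumor Measurement row to select patients without prior progression, while the Radiology row has an entry without that limit.

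**The concern.** The first problem is that two instructions cover the same patient and give different answers. Whether a responding patient who needs more than 6 weeks to recover may restart depends on which paragraph the site follows. With two sites, they could handle the same case differently.

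The second problem concerns follow-up. An intent-to-treat PFS analysis needs progression to be looked for at the same interval whether or not the patient is still on drug. If scanning stops with dosing, a patient who stops without progression either has progression recorded at the one-year scan or is censored at the last scan. These patients are selected by toxicity, so censoring cannot be assumed to be unrelated to outcome. The gap applies to any stop without progression, not only to 6-week holds.

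**Working it through.** **Do the rules meet in one patient?** The triggers differ: Section 2.7 looks at unrecovered toxicity, the Section 3.3 bullet at interruption of cabozantinib, and the Section 3.3 paragraph at interruption of both drugs. That paragraph stops both drugs for a toxicity of either. A related toxicity that stays intolerable beyond 6 weeks therefore meets all three. Two allow a restart for benefit and the third does not.

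Such holds are plausible on the protocol's own text. For other severe pembrolizumab toxicity treated with corticosteroids, Section 3.4.1 asks for a taper of at least 1 month after improvement to grade 0 or 1, with restart afterwards. One month is about 4.3 weeks, and 6 − 4.3 = 1.7. If improvement takes more than about 2 weeks, the hold passes 6 weeks.

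The allowance for non-AE holds is different. The joint-hold mechanism works through toxicity, so that allowance conflicts with the removal rule only if both drugs happen to be held for such a reason.

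**Scans lost if a site follows Table 16-1.** Inputs: scans every 9 weeks from C1D1, so weeks 9, 18, 27, 36 and 45; the one-year scan taken as week 52 from C1D1 (an assumption); removal at hold start + 6 weeks; no restart. Reading A continues scans until removal. Reading B stops them at the last dose, as Section 16 defines the Treatment Period. Lost = scheduled scans after the last one done. Gap = 52 − week of last scan.

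| Hold starts | Removed | A: last scan | A: lost | A: gap | B: last scan | B: lost | B: gap |
|---|---|---|---|---|---|---|---|
| 2 | 8 | baseline only | 5 | – | baseline only | 5 | – |
| 6 | 12 | 9 | 4 | 43 | baseline only | 5 | – |
| 12 | 18 | 18 | 3 | 34 | 9 | 4 | 43 |
| 24 | 30 | 27 | 2 | 25 | 18 | 3 | 34 |

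So 2 to 5 scans are lost. Under reading A, holds starting at weeks 6 to 24 give gaps of 43 to 25 weeks instead of 9.

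**What this could do to PFS (illustration only).** The documents give no rate of such stops for the combination. With 34 patients and no other censoring, each patient who has progressed but is still counted event-free adds 1/34 = 2.9 percentage points to the curve at that time.

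For a range, assume exponential PFS and let a share q of patients stop with equal chance just after the week 9, 18 or 27 scan, if not yet progressed, with the next scan at week 52. Week-27 PFS then rises by q × [(S9 − S27) + (S18 − S27) + 0]/3.

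- Median 12.3 weeks. This matches the 6-month PFS of 23% reported for pembrolizumab alone in Section 1.1: 26 × ln 2 / −ln 0.23 = 12.3. S9, S18 and S27 are 60.2%, 36.3% and 21.8%. The bracket divided by 3 is 17.6 points. For q of 10% to 30%, 21.8% becomes 23.6% to 27.1%.
- Median 26 weeks (assumed). S9, S18 and S27 are 78.7%, 61.9% and 48.7%, and the bracket divided by 3 is 14.4 points. 48.7% becomes 50.1% to 53.0%.

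A simulation of the same setting that censored these patients at the last scan instead changed week-27 PFS by no more than about 0.1 point. That result assumes that stopping is unrelated to prognosis, which a toxicity stop need not be.

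**The case against.** The strongest reply is that the text, read whole, already does what is wanted. The removal sentence goes on to keep response data and intent-to-treat PFS. Section 2.2.1 provides a Post-Treatment Period, and the table has 3-monthly visits. Removal may therefore mean off treatment but still followed. That is a fair reading and probably the intent, but the words do not say it, and it supplies neither the missing exception nor the missing scans.

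On imaging, footnote i speaks of scans during treatment but explains this as after baseline and counts from C1D1, so it is weak evidence for an on-drug limit. This stands. The narrower reading rests on the column heading, the definition of the Treatment Period and the separate one-year entry, which would be largely redundant if 9-weekly scanning continued off drug.

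The sponsor might also prefer a strict limit, since Section 1.3 cites poor tolerance of the combination at a higher cabozantinib dose. That is a legitimate choice, but the exceptions in Section 2.7 and the Section 3.3 bullet would then have to go.

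The different approvers are not a contradiction, because both can be satisfied; they only need aligning.

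A reader might infer that the removal rule also overrides every long surgical hold. The documents do not support this: nothing there stops pembrolizumab when only cabozantinib is held for surgery. Nor do they support the inference that there is no imaging after treatment, because the one-year scan is scheduled and its Radiology entry is unrestricted.

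**Conclusion.** The point holds in two limited parts. First, the removal rule for holds of more than 6 weeks conflicts with the benefit exception in Section 2.7 and in the earlier bullet of Section 3.3. The non-AE allowance conflicts only when both drugs are held. Second, the sections differ on imaging after a stop without progression, and a site following Table 16-1 would next image such a patient at one year.

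The consequence is late-dated or censored progression in the secondary PFS estimate. The scan counts follow from the schedule, given the one-year scan at week 52. The size of the PFS effect cannot be derived, because the number of such patients is unknown; the percentages above rest on assumed shares and an exponential curve.

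A reader might infer that the primary ORR decision is affected, since a patient who stops before week 9 has no early scan under the table and could drop out of the evaluable set. Section 18 accepts any follow-up scan, so this is not established, and no effect on the go/no-go rule is shown. The text should be corrected, but the problem does not undermine the trial.

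**What to change.** In the Section 3.3 paragraph, replace removal from the study with: *will be discontinued from study treatment, unless there is unequivocal evidence of benefit and the principal investigator/Sponsor agrees to a restart (Section 2.7), and will remain in follow-up*. Add that the non-AE allowance in Section 3.3 also applies when both drugs are held for such a reason. Name the same approver in the Section 3.3 bullet on related AEs.

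In Table 16-1 and footnote i, state that patients who stop treatment without progression continue tumor assessments every 9 weeks from C1D1 until progression, new anticancer therapy, death, withdrawal of consent or end of study follow-up. State that PFS is censored at the last scan before new anticancer therapy.

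The cost is amendment wording plus about 2 to 5 more scans per such patient in the first year, and further scans if the patient stays progression-free beyond it. This is the interval that the synopsis and Section 2.2.1 already state.
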